To compare the overall cost of post-operative rehabilitation of patients involved in traditionally employed regimens versus those using the StepRite device.

Hypothesis and specific aims

The aim of this study is to evaluate whether improved clinical outcomes as well as reduction in cost in provision of care can be better affected through the use of the Steprite device as compared to the use of traditional rehabilitation modalities.

We will seek to reject the null hypotheses that 1) there is no difference between clinical outcomes attained between patients using the Steprite device and those using traditional rehabilitation modalities and that 2) there is no reduction in cost to the medical system when patients use Steprite versus other conventional methods of rehabilitation.

By rejecting the null hypothesis we will accept the alternate hypothesis that, through the use of the Steprite device, not only will patients achieve overall clinical outcomes faster but there will be an associated decrease in cost burden to the medical system and the differences observed will be statistically significant as compared to rehabilitation of patients not using the Steprite device.

Patients who use the device post-surgery will demonstrate superior short-term improvements (i.e. 3 months post-surgery) with respect to self-reported functional outcomes and gait parameters, compared to a control group not using the device. The patients will self-report through the use of validated survey instruments including the KOOS survey (knee injury and osteoarthritis outcome score), LEFS (lower extremity functional scale) and/or KSS (knee society score), the latter of which includes a section for surgeon evaluation of patient functionality post operatively.

Study Design and Methods

This is a point of care clinical trial; a trial that functions to integrate research within a clinical setting that has the ability to readily deliver either modality of the proposal. This type of study design relies on provider referral of patients to be approached for consent, after which randomization to one of two treatment groups is facilitated; a control group of 15 patients participating in conventional rehabilitation regimens and an experimental group of 15 patients who will participate in the same rehabilitation regimen but facilitated

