through the use of Steprite. Importantly, care for patients is delivered as part of current adopted standards utilizing outcome measurements, the use of which and the interpretation of which is already built into care provided by the clinical facility, thereby negating the need to develop additional outcome measures. Recruitment of 30 patients will come from the investigators' normal patient population, among patients who are scheduled for partial or total knee arthroplasty. As there is no change in post op care for these patients from the investigators standard protocols other than monitoring and enforcement of home protocols, the same therapists involved in investigators' normal patient care will be involved with both arms of the study.

For this study, 30 patients represents a sample size deemed acceptable as a starting point. There are no other published studies using Steprite in comparative design trials. Determinations of sample size needed for this study, using 80% power and significance of 0.05, incorporate the use of a time frame in days or weeks for completion of the rehabilitation protocols that would allow for the detection of clinically significant differences between the group using Steprite and those using conventional therapies only. Given that conventional therapies can include skilled nursing, home health and outpatient visits and given that the need for each of these is highly variable dependent on the patient, it is difficult to assign a time value for determinations of sample size.

With that, a sample size of 30 participants divided into two groups represents an initial starting point, with the potential of incremental addition of more patients in order to achieve significance between the two study groups.

Statistical significance will be evaluated utilizing a standard t-test for two group comparison.

In preparation for the study, MedHab Inc. will at their expense train all involved investigators and therapists in the fitting and use of the StepRite device. Medhab will also train a lead therapist designated by the lead investigator to be in charge of overseeing and monitoring, ensuring proper use of the device. There is no cost to the patient, hospital or other funding entity for participation in this study. Medhab LLC will assume all costs associated with the training, application, device and use of the StepRite product for the full course of this study.

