Subjects for this study will be recruited from the patient population seen by the investigators during the normal course of business. There will be no outside recruitment of individuals or advertising as to the presence or use of the monitoring device to entice new patient referral. Prospective candidates will be asked by the lead investigator at the time they are designated surgical candidates. All documentation related to the study will be reviewed with the patient by the lead physician or his designee who is appropriately trained in discussing patient recruitment. Final decision and randomization to control or StepRite use will be done as part of the preoperative checkup just prior to surgery where both operative consent and study consent are discussed and signed.

Randomization:

Once a patient agrees to the study they would be sequentially randomized into whether or not they receive StepRite. The patients will be randomized to every other eligible patient gets the intervention. (ie: 1,3,5,7,9... will get StepRite ; 2,4,6,8 will not get StepRite) 15 Intervention subjects will be recruited and 15 control subjects will be recruited with an extra 5 patients to account for attrition and withdrawals.

Schedule of events

The intervention group will receive the StepRite device with standard conventional care and the control group will receive standard conventional care only. Both groups will receive outpatient, home health, and /or 24 hour physical therapy treatment plans per their surgeon's standard of care. The control group will undergo the conventional outpatient treatment program to 8 weeks as normally prescribed by the lead investigator. This consists of a twice weekly outpatient appointment with a physical therapist and prescribed home exercise program (see attached physical therapy protocol).

The patients randomly selected to wear the StepRite inserts will be fitted and instructed along with the patient's designated care giver in their use including initial pre-op measurements prior to their surgical date so that data collection can begin on the 1st day of rehab after surgery

Those patients not selected to wear step rite will receive instructions preoperatively of their expected therapy regimen and receive their baseline functional evaluation of the knee

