The patient or designated care giver will be responsible for placing the insoles on their charging platform nightly.

Indicate the number of patients/charts/surveys/specimens needed.

The total number of patients needed in this study is 30, we will request a total of 35 to account for possible Attrition or withdrawals. 15 will be fitted with the StepRite device and 15 will follow the normal postoperative protocol without the device and be considered control subjects.

Inclusion criteria

Unilateral Partial or Total knee arthroplasty.

Age 45-75 yr. old

BMI <35

Access to Wi-Fi

Have appropriate smart phone and knowledge of use

Be willing to place StepRite app on their personal phone

Exclusion criteria

History of neuromuscular disorder (e.g. Parkinson's, Polio, or stroke).

Pregnancy

History of cognitive disease that would preclude ability to navigate smart phone

Method of identifying and recruiting subjects.

Recruitment will come from the investigators normal patient population who are scheduled for a partial or total knee replacement. The Investigators will identify and consult the research coordinator to assess eligibility.

Compensation given to subjects.

There will be no compensation given to subjects. They will be allowed to keep the insoles and access the app for at home therapy at no cost to them for as long as the device works.

Describe the site(s) where study will be done.

The main clinical/surgical portion of the study will take place at Texas Tech University Health Sciences Center department of Orthopaedic Surgery and University Medical Center Lubbock. The physical therapy departments used for this study will be the investigators preferences and standard of care, therefore they would be used if not on the study and are not study specific.

MedHab LLC (StepRite) will be collecting data from several sites to compare outcomes and cost. The secondary sites utilizing this device and doing similar studies are Covenant with [name] as the lead investigator, the Lubbock Heart Hospital with [name] as the lead investigator, and Texas Health Resources with [name] as lead investigator. All the secondary sites will use their standard of care preferences for clinical/surgical and physical therapy. TTUHSC will not be collecting data nor in any way be affiliated with the secondary study sites. They will acquire their local IRB approval for each site separately using similar device protocols.

Risks

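### The protocol allows patients to be added until the result is significant, using an unadjusted t-test, so the 5% false-positive rate is lost if that option is used

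*Combined protocol and SAP*

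**What the plan says.** The sample-size text in Study Design and Methods accepts 30 patients as a beginning and then permits enlargement "with the potential of incremental addition of more patients in order to achieve significance between the two study groups". It mentions the usual design parameters ("Determinations of sample size needed for this study, using 80% power and significance of 0.05") but says that a time value for the calculation is hard to assign. No difference to detect and no SD are given, and the text does not claim that 30 patients provide 80% power.

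The analysis plan is one sentence: "Statistical significance will be evaluated utilizing a standard t-test for two group comparison".

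The other enrolment figure is 35. Randomization recruits 15 per arm "with an extra 5 patients to account for attrition and withdrawals", and the section on the number of patients needed says "we will request a total of 35 to account for possible Attrition or withdrawals". Both tie the extra five to losses. Neither calls 35 a ceiling or links it to the extension.

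Hypothesis and specific aims sets out to reject two nulls. The first is that "there is no difference between clinical outcomes attained between patients using the Steprite device and those using traditional rehabilitation modalities"; the second is that the device brings no cost reduction.

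**The concern.** The stated purpose of adding patients is a significant result. It is not a target precision, a target power or a blinded variance estimate. To know whether significance has been reached, someone must run the test. If the result is not significant, the clause permits more enrolment and another test at the same 0.05. Each repeat gives chance another opportunity, and with no maximum the cumulative false-positive probability rises with every look.

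This matters because the protocol is written to reject null hypotheses. A p-value below 0.05 reached after one or more extensions would not carry the error rate that it appears to carry. Nothing in the plan requires the number of earlier looks to be fixed or reported, so a reader could not correct for them.

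**Working it through.** **Inputs.** From Study Design and Methods and Randomization: 15 per arm at the first test, 1:1 allocation, level 0.05, ordinary t-test. From Randomization and the section on patients needed: 35 in total, which alternation splits 18/17. Assumed, because the protocol is silent: two-sided testing, normal outcomes with equal variances, one endpoint, stopping at the first p<0.05, and the look schedules below.

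**The plan's own figure.** The 30 cannot be reproduced, because no effect size or SD is given. What 15 per arm can do follows from the noncentral t distribution with 28 degrees of freedom and noncentrality d·√(15/2):

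- 80% power requires d = 1.06 SD.
- Power is 56% at d = 0.8 and 26% at d = 0.5.
- The 95% CI half-width is t(0.975, 28)·√(2/15) = 2.048 × 0.365 = 0.75 SD.

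With a true difference of 0.5 SD, the first test would therefore be non-significant about 74% of the time (1 − 0.26). The extension option is likely to come into play unless the effect is very large.

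**Two looks, approximate formula.** Under the null, the two test statistics have correlation ρ = √(I₁/I₂), with I = 1/(1/n₁ + 1/n₂). The overall type I error is 1 − P(|Z₁| < 1.96 and |Z₂| < 1.96).

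- 15/15 then 18/17: I₁ = 7.5, I₂ = 8.74, ρ = 0.926, error 6.8%.
- 15/15 then 20/20: I₂ = 10, ρ = 0.866, error 7.3%.
- 15/15 then 30/30: I₂ = 15, ρ = 0.707, error 8.3%.

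**Simulation with the actual t-test.** 400,000 null trials per schedule (200,000 for steps of 10 per arm):

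| Tests made, stopping at the first p<0.05 | Type I error |
|---|---|
| Once, at 15/arm | 5.0% |
| At 30 and 35 patients | 6.7% |
| After every patient from 30 to 35 | 8.1% |
| At 15 and 20/arm | 7.4% |
| At 15 and 30/arm | 8.3% |
| Steps of 5/arm, to 30/arm | 10.7% |
| Steps of 5/arm, to 45/arm | 14.1% |
| Steps of 5/arm, to 60/arm | 16.5% |
| Steps of 10/arm, to 25/arm | 8.1% |
| Steps of 10/arm, to 45/arm | 12.0% |

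Independent reruns agreed to within about 0.2 percentage points.

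**Levels that restore 5%.** A constant per-look threshold of about 0.029 for looks at 15 and 30 per arm, or about 0.022 for looks at 15, 20, 25 and 30 per arm, brings the overall error back to about 5%.

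**The case against.** **Retesting is inferred.** No interim analysis is described. The clause follows an admission that no comparative data exist, so it could mean only that more patients may be enrolled if 30 proves too few. If that were decided without seeing the comparison, 5% would hold. This is why the inflation is stated conditionally. But the stated aim is to achieve significance, which points to a decision driven by the test result, and nothing in the text rules that out.

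**The documents contain no number above 35.** This is true. The figures for 45 and 60 per arm (90 and 120 patients) rest on assumed schedules. However, 35 is an allowance for losses and not a limit on the extension. Even read as a limit, it gives 6.7% with one retest. The 8.1% for testing after every patient is an extreme case, since outcomes accrue over weeks.

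**A single test does not settle every error-rate problem.** This also stands. The protocol lists KOOS, "LEFS (lower extremity functional scale) and/or KSS (knee society score"), gait and cost without choosing a primary. With one look and independent endpoints, the chance of at least one false positive is 1 − 0.95³ = 14% for three and 1 − 0.95⁵ = 23% for five. With an assumed correlation of 0.7, simulation gives about 11% and 15%. That is a separate gap. It does not excuse the extension clause, but it means that the 5% for a single analysis applies to each endpoint and not to the trial as a whole.

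**Sidedness is not stated.** The cost null reads as one-sided. This changes little: tested one-sided at 30 and then 35 patients, the error is 6.6%.

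**Conclusion.** The concern holds, and the clause must be changed. As written, the protocol permits sampling until significance with an unadjusted test. If the option is used after a non-significant result, type I error for one endpoint is about 6.7% when 35 is treated as a ceiling with one retest, and 8.3% for a single doubling. It passes 10% under repeated small extensions, with no upper limit set by the plan. The exact figure depends on the assumed looks, but every extension schedule tried exceeded 5%. A single analysis at a fixed size, or an extension decided without sight of the group comparison, would keep 5% for that endpoint. Once unplanned looks have been taken, the problem cannot be repaired afterwards.

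**What to change.** Delete the clause on incremental addition in Study Design and Methods and replace it with wording such as:

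> *Enrolment is fixed at 35, with the aim of 30 evaluable patients (15 per arm). Each comparison is tested once, after the last enrolled patient completes follow-up, at two-sided 0.05, and is reported as an effect estimate with its 95% CI. No patients will be added on the basis of results.*

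Add, as a clarification, that 15 per arm gives 80% power only for a difference of about 1.06 SD. The sponsor should confirm that two-sided testing is intended for cost as well. Naming one primary endpoint and time point would be good practice here too, for the multiplicity reason above.

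If expansion must remain possible, a primary endpoint becomes essential. Then choose one of two routes:

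- base any increase only on the pooled SD, with group labels hidden; or
- pre-specify the looks, the maximum sample size and a group-sequential boundary, for example a per-look threshold of about 0.029 for looks at 15 and 30 per arm, or 0.022 for looks at 15, 20, 25 and 30 per arm.

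**Cost.** The main fix changes wording only. The hypotheses can stay, and the numbers are those already requested. The sponsor gives up the open-ended option to extend. Keeping expansion costs more: a primary endpoint must be chosen and, on the group-sequential route, each look must meet a stricter threshold.

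### The plan's only test, a two-group t-test, is tied to no outcome or week; no outcome is primary, and no survey is expressly scheduled at the hypothesised 3 months

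*Combined protocol and SAP*

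**What the plan says.** The analysis is one sentence, under Study Design and Methods: "Statistical significance will be evaluated utilizing a standard t-test for two group comparison". It gives no outcome, no time, and no choice between final value and change. Other sections suggest several outcomes, none of them called primary:

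- Hypothesis and specific aims sets two null hypotheses, one on unspecified clinical outcomes and one on cost. The alternative is that "not only will patients achieve overall clinical outcomes faster", together with a lower cost burden.
- The same section expects "superior short-term improvements (i.e. 3 months post-surgery) with respect to self-reported functional outcomes and gait parameters", self-reported through the "KOOS survey (knee injury and osteoarthritis outcome score), LEFS (lower extremity functional scale) and/or KSS (knee society score").
- The sample-size text in Study Design and Methods refers to a "time frame in days or weeks for completion of the rehabilitation protocols", then says a value is hard to assign.

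On timing, the Device Flow Chart names surveys (KOOS, KSS, LEFS) at week 2 in clinic and at weeks 4, 6 and 8 in physical therapy. It places investigator visits at weeks 2, 6 and 12. Schedule of events gives both groups routine KOOS and KSS at regular clinic visits, without weeks and without LEFS. It also describes outcome measurement at clinic visits up to 8 weeks.

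Before surgery, Schedule of events gives the device arm fitting and instruction, "including initial pre-op measurements prior to their surgical date", and gives controls a baseline functional evaluation of the knee. The visible text schedules no preoperative survey common to both arms. The attachments are not shown and may say more.

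**The concern.** The plan intends to reject null hypotheses at 0.05, so a reader must be able to tell which comparison decides the first one. Here it could be any of two or three instruments, a gait measure, speed of attainment or time to completion, and the and/or in the instrument list leaves even the set of scores open. A t-test on one score at one week tests neither speed of attainment nor time to completion.

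Two further gaps follow. The hypothesised time is 3 months, but the last named survey week is 8, so the central claim may rest on data that no passage expressly schedules. And improvement implies change from a starting value, yet the two arms' preoperative assessments are described differently and neither is named as a survey. With 15 per arm, having a common baseline score, and how it is used, alters the difference the trial can detect.

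**Working it through.** **1. The plan's own figure.** The total of 30 (15 per arm) cannot be reproduced, because no outcome, difference or standard deviation (SD) is given. The plan states 80% power and significance 0.05. It does not state sidedness, so two-sided is assumed. Working back with the noncentral t distribution (28 degrees of freedom, noncentrality d × √(15/2)), 80% power requires d = 1.06 SD. A one-sided test would give 0.93 SD.

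**2. Which test does the sentence mean?**

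| Source | Outcome type | Time |
|---|---|---|
| First null hypothesis | clinical outcomes, unnamed | none |
| Alternative | speed of attainment | none |
| Superiority statement | KOOS, LEFS and/or KSS; gait | 3 months |
| Sizing text | time to complete rehabilitation | days or weeks |
| t-test sentence | none | none |

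**3. Is a 3-month score collected?** Named survey weeks are 2, 4, 6 and 8. Routine KOOS and KSS at regular clinic visits, read with the 12-week investigator visit, could supply week 12 in both arms. No passage makes that link, and LEFS is not in the both-group list.

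**4. Error rate for the first null hypothesis at one visit.** This is conditional on any one significant score being enough. With k independent tests the chance of at least one false difference is 1 − 0.95^k: 9.8% for k = 2 and 14.3% for k = 3. Scores from the same patients are correlated, so null trials were simulated (15 per arm, pooled t-test, two-sided 0.05, common correlation r assumed):

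| Instruments | r = 0.8 | r = 0.5 |
|---|---|---|
| 2 | 7.9% | 9.2% |
| 3 | 10.1% | 12.7% |

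About half of each figure favours StepRite (3.8-4.7% and 5.1-6.3%), against 2.5% nominal. Choosing among visits as well would raise these further.

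**5. Detectable difference at 80% power, 15 per arm, two-sided 0.05,** by assumed baseline-outcome correlation ρ:

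- t-test on the score: 1.060 SD at any ρ.
- t-test on change: 1.060 × √(2(1 − ρ)).
- ANCOVA: 1.061 × √(1 − ρ²) × √(1 + 1/26), where 1.061 is the step 1 value recomputed with 27 degrees of freedom.

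| ρ | Score | Change | ANCOVA |
|---|---|---|---|
| 0.3 | 1.06 | 1.25 | 1.03 |
| 0.5 | 1.06 | 1.06 | 0.94 |
| 0.7 | 1.06 | 0.82 | 0.77 |

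For example, at ρ = 0.5 ANCOVA gives 1.061 × 0.866 × 1.019 = 0.94. Simulation of the ANCOVA case gave power of 0.80 to 0.81 and type I error of 0.050 to 0.051.

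**The case against.** **A reader might infer that no 3-month data will exist.** The documents do not support that. Routine KOOS and KSS at regular clinic visits plus a 12-week visit is a natural joint reading. The sentence ending outcome visits at 8 weeks concerns detecting delayed progress and does not expressly close efficacy follow-up. What stands is that the 12-week survey is never stated.

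**A reader might infer that controls are not surveyed on LEFS.** That also goes too far. The surveys sit under a heading about standard post-operative care, and Control Subject flow gives controls the same care as the device group. But the surveys are described as added to standard care, so LEFS in controls is not assured.

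**A reader might count three instruments at four weeks, 12 tests, and quote a false-positive chance of 19-36%.** Those weeks are not the hypothesised 3 months, and no passage says that any one significant result suffices. The figure cannot be presented as the plan's error rate. The single-visit figures rest on the same unstated rule, but they match the stated hypothesis. None of these figures is the chance of falsely making the joint claim, which also requires lower cost.

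**The t-test may be meant for time to completion.** This is plausible, since that is the only variable discussed for sizing. The plan neither says so nor calls it primary, so the choice is the sponsor's.

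**Improvement might be judged from the measurements just after surgery and at discharge.** They are not named as surveys, and they follow both surgery and assignment, so they are no substitute for a preoperative score.

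**ANCOVA is a preference.** This is partly right. The gain over the score t-test is only 0.03 SD at ρ = 0.3, and a t-test on a named score is valid.

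**Conclusion.** The point holds as a gap in specification. The sole test is linked to no outcome or week, no outcome is primary, and the hypothesis, sizing text and survey schedule point to different comparisons. The 3-month survey is plausible but unstated.

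If any one significant score at the hypothesised visit were enough, the first null hypothesis would be falsely rejected about 8-9% of the time with two instruments and 10-13% with three. This assumes two-sided 0.05 and correlations of 0.8 to 0.5. The plan neither states nor excludes that rule. With a common preoperative score, ANCOVA would lower the detectable difference from 1.06 SD to between 1.03 and 0.77 SD, for assumed ρ of 0.3 to 0.7. This should be corrected before analysis. Confidence is medium, because the attachments could not be seen.

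**What to change.** 1. Name one primary outcome at one week, collected in both arms, and tie the test to it. The sponsor chooses between a score and time to completion (which would be defined by its end event, not a week). Restate the first null hypothesis and the sizing sentence on that outcome, and state sidedness.
2. If it is a score at 3 months, state that both arms complete that survey at the existing 12-week visit. Otherwise restate the hypothesis at week 8. State that controls complete the same surveys in the same weeks, and whether LEFS is included.
3. State that cost is a separate hypothesis, and how it counts towards the joint claim of faster outcomes and lower cost. Label the other instruments, visits, gait and speed of attainment secondary, either Holm-adjusted or without a significance claim.
4. For a score, preferably give both arms the same questionnaire at the existing preoperative checkup, before assignment is disclosed. The protocol places assignment there too: "Final decision and randomization to control or StepRite use will be done as part of the preoperative checkup just prior to surgery". Suggested text: *The primary comparison is the between-arm difference in [named score] at [named week], estimated by ANCOVA with the preoperative score as covariate, two-sided 0.05.* Without a common baseline, state a t-test on the named score.

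The cost is wording, one or two extra questionnaires at existing visits, one degree of freedom, and loss of the choice of which result to headline. Two separate issues remain: the option of "incremental addition of more patients in order to achieve significance", which naming a primary does not control, and the predictable alternating assignment, which also limits how well a preoperative questionnaire can be kept blind to arm.
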